5.1.7 V11 (month 9), V12 (month 12) – All Cohorts – PERIOD II

This period will consist of 2 visits at Months 9 and 12. Month 9 visit will be conducted on day 4(-1) after MOD-4023 dosing for MOD-4023 dose cohorts, and any day during the week for

¹ Delta height SDS at least 0.2

OPKO Biologics	Protocol for Clinical Study CP-4-004	Page 57 of 133
Effective Date: Date of final electronic approval		

Genotropin cohorts. Month 12 visit (final visit of the Main Study) will be conducted 4 days (-1) after the last MOD-4023 dose for MOD-4023 cohorts and the day after the last Genotropin dose for Genotropin cohorts. Period II assessments will include the following at each visit:

1. Physical examination and vital signs;
2. AEs, local tolerability, and concomitant medications;
3. Parameters of glucose metabolism: fasting glucose, insulin, and HbA1c;
4. Other hormonal levels: TSH, free T4, free T3, cortisol;
5. Antigenicity: anti MOD-4023 antibodies/anti-hGH antibodies (only month 12 visit);
6. Routine safety biochemistry, hematology, and urinalysis parameters;
7. Patient's height;
8. Patient's weight;
9. Parameters of lipid metabolism at both visits (with Lp(a) lipoprotein at month 12 only);
10. Pubertal status (only month 12 visit);
11. PD: IGF-I and IGFBP-3 serum levels;
12. MOD-4023 (cohort 1-3) and Genotropin (cohort 4) serum levels;
13. Fundoscopy (Month 12 only or earlier if there are signs or symptoms indicative of benign intracranial hypertension);
14. ECG (Month 12 only);
15. Bone age (Month 12 only).

At the end of Period II, a formal data analysis of all endpoints will be performed.

5.2 12-MONTH OPEN LABEL EXTENSION (OLE) PERIOD III

Visits (Visit 1 OLE/Day 1, Visit 2 OLE/Month 1, Visit 3 OLE/Month 3, Visit 4 OLE/Month 6, Visit 5 OLE/Month 9 and Visit 6 OLE/Month 12)

Patients who completed 12 months of treatment in the Main Study will be eligible to continue to a 12-month OLE period. Patients who received MOD-4023 in the Main Study (initial 12 months of active treatment) will continue to receive MOD-4023; dose will be same as in the Main Study. For these patients, study visits will take place every 3 months, starting at visit 3 OLE.

For these patients, V12 of the Main study will be considered as the first visit of the OLE phase in which the patient will receive the study drug for the next 3 months of the OLE.

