The following assessments will be conducted every 6 months (± 2 weeks) on day 4 (-1) post dose on top of the 3 month assessments:

- IGF-I, IGFBP-3 and MOD-4023 serum levels.
- Once a year, patients will be required to attend another visit **on dosing day** (in addition to the semi-annual visit on day 3 or 4 post dosing) where the following additional assessments will be conducted (on top of the three and six months assessments):Anti-MOD-4023 antibodies;
- MOD- 4023 serum levels
- Physical examination;
- Vital signs;
- Parameters of glucose metabolism (fasting glucose, fasting insulin and HbA1c);
- Other hormonal levels (TSH, free T4, free T3, cortisol);
- Parameters of lipid metabolism;
- Routine safety laboratory (biochemistry, hematology and urinalysis);
- Pubertal status;
- ECG;
- Bone age;
- For males above the age of 13 - LH, FSH and testosterone. For females above the age of 12 - LH, FSH and estradiol;
- Fundoscopy (if indicated).

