5.4.2 Second year of LT-OLE-PEN until marketing approval

From the second year of the LT-OLE-PEN period and until marketing approval, visits will be conducted every 3 months, \pm 2 weeks (months 3, 6, 9 and 12) on day 4 (-1) post injection. The following will be conducted at each visit:

- Auxology measurement (actual height measured on calibrated stadiometer);
- Body weight measurement;
- Adjustment of dose for weight;
- AEs;
- Local tolerability;
- Concomitant medications;
- Dispensing of drug and return of used drug;
- Fundoscopy (if required);
- IGF-I and IGFBP-3;
- Physical examination and vital signs;
- Urine pregnancy test for females of child bearing potential (in case of positive result please refer to section [7.4](#));
- Pubertal status;
- Provide patient diary and return of completed diaries;

In addition, the following will be conducted every 6 months, on month 6 and month 12 visits:

- MOD-4023 serum levels;
- Anti MOD-4023 antibodies;
- Parameters of glucose metabolism (fasting glucose, fasting insulin and HbA1c);
- other hormonal levels (TSH, free T4, cortisol);
- Parameters of lipid metabolism;
- Routine safety laboratory (biochemistry, hematology and urinalysis);

In addition, the following will be conducted once a year, on 12 month visit:

- ECG;
- Bone age;
- For males above the age of 13 - LH, FSH and testosterone. For females above the age of 12 - LH, FSH and estradiol

OPKO Biologics	Protocol for Clinical Study CP-4-004	Page 66 of 133
Effective Date: Date of final electronic approval		

Throughout the LT-OLE-PEN period, patients will continue to complete a patient diary at home to collect dosing and safety data.

If splitting the dose between 2 different injections, the Patient should complete new diary page for each PEN or injection:

Weekly dose	Number of patient Diary pages
1 injection	1
2 injections from the same pen	2
2 injections from 2 different pens	2

The investigator may conduct unscheduled visits, for safety reasons, or any other reason per investigator medical judgment.

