OLE PEN	Every 3 months OLE visit - day 4 (-1) post dose	Every 6 months OLE visit – day 4 (-1) post dose	Every 12 months OLE and EOS when marketing approval received - on dosing day/ from second year, visits are done on day 4 (-1) post dose
Auxology measurements: Actual HT measured on a calibrated stadiometer and body weight measurement	Х		
Adjustment of dose for weight	X		
AEs	X		
Local tolerability	Х		
Concomitant medication	Х		
Dispensing of drug	Х		
Return of used drugs	X		
IGF-1, IGFBP-3	Х		
Somatrogon serum levels	Х	X -from second year	Х
Anti-somatrogon antibodies	X	X -from second year	
Physical examination	X		
Vital signs	X		
Glucose metabolism (fasting glucose, fasting insulin and HbA1c)	X ⁵	X – from second year	
Other hormonal levels (TSH, FT4, T3, cortisol)	X ⁵	X – from second year	
Parameters of lipid metabolism	X ⁵	X – from second year	
Routine safety laboratory (biochemistry, hematology and urinalysis)	X ⁵	X – from second year	
Urine pregnancy test	Х		
Pubertal status	Х		
ECG around Tmax (7-12 hours post dose) ⁷			Х
BA			X
LH, FSH and testosterone. ³			X
LH, FSH and estradiol ⁴			X

⁵ Data collected every 3 months with the exception of month 9.
³ For male patients that are on the age 13 years old and above
⁴ For female patients that are at the age of 12 years old and above

Long-Term OLE PEN (LT-OLE-PEN) Period V From 2nd Year Until Marketing Approval

	LT OLE PEN	visits by Month ove	er each year the stu	ıdy is running
	Month 3 visit (±2 week)	Month 6 visit (±2 week)	Month 9 visit (±2 week)	Month 12 (±2 week) ⁵
Assessments	day 4 (-1) post dose			
Auxology measurements: actual height measured on calibrated stadiometer	Х	Х	Х	Х
Body weight measurement	Х	Х	Х	Х
Adjustment of dose for weight	Х	Х	Х	Х
AEs	Х	Х	Х	Х
Local tolerability	Х	Х	Х	Х
Concomitant medication	Х	Х	Х	Х
Dispensing of drug	Х	Х	Х	Х
Return of used drugs	Х	Х	Х	Х
Fundoscopy - If required	Х	Х	Х	Х
IGF-I, IGFBP-3	Х	X	Х	Х
MOD- 4023 serum levels		X		Х
Anti-MOD-4023 antibodies		Х		Х
Physical examination	Х	Х	Х	Х
Vital signs	Х	Х	Х	Х
Glucose metabolism (fasting glucose & insulin, HbA1c)		Х		Х
Other hormonal levels (TSH, free T4, cortisol)		Х		Х
Parameters of lipid metabolism		Х		Х
Routine safety laboratory (biochemistry, hematology and urinalysis)		Х		Х
Urine pregnancy test ⁶	Х	X	Х	Х
Pubertal status ⁷	Х	X	Х	Х
ECG				Х
Bone age				Х
LH, FSH and Testosterone ⁸				X

⁵ In case ET/EOS visit is conducted all assessment should be done as one with no split.

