6 CONVENTION FOR REPORTING TREATMENT PERIODS

Periods III and IV: The protocol defines Period III as a 12 month period when patients are in three specific dose groups, and Period IV as starting on 0.66 mg/kg/week after 12 months in Period III. Because of the differences in timing of transition to the 0.66 mg/kg/week dose, all data from Periods III and IV will be presented in 12 month intervals, starting with the first dose of treatment at the start of Period III. The dose at the beginning of each 12 month period will be used to classify the patient to a dose group for disposition purposes. For the first 12 months, the results will be reported by the assigned dose group. After the initial year on OLE, all patient results will be summarized in a single treatment group, regardless of assigned dose level, or any individual patient dose adjustments.

Period V: This period will contain data from patients on PEN treatment. Baseline data for this period will be the data collected at the visit for the first PEN dose, prior to the first PEN dose.

The cumulative change in HT SDS from the start of treatment in Period I will also be summarized. For these summaries, the original dosing assignment will be used, and the reporting periods will be at each of the scheduled Month 12 visit of the period. Gaps in treatment will be included, so that the elapsed time may be longer than 12 months.

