9.6 Laboratory Test Results

Clinical laboratory measurements will be summarized with descriptive statistics at each visit. Changes within each 12 month period will use the first visit of the 12 month period as the baseline. For Period V the baseline will be the first visit with PEN injection. If data from the first visit of each period are not available, the last previous visit data will be used. Summary of abnormal results (reported as low, high, clinically significant) will be provided for each 12 month period, with the number of patients at the beginning of each period for the denominator.

The following laboratory results will be presented:

Glucose Metabolism	Endocrinology	Lipid Metabolism
Fasting blood Glucose	FT4	Cholesterol
Fasting Insulin	Т3	High density lipoprotein (HDL)
HbA1c	Thyrotropin (= TSH)	Low density lipoprotein (LDL) Cholesterol
	Cortisol, Free	Lipoprotein-A
	Females >=12 y.o.: FSH, LH and estradiol	Triglycerides
	Male >=13 y.o.: FSH, LH and testosterone	

Glucose Metabolism, Endocrinology, and Lipid Metabolism:

Clinical Chemistry	Hematology	Urinalysis
Albumin	Differential Blood Count of Leukocytes	Bilirubin
Alkaline phosphatase	Erythrocyte Count	Glucose
Calcium	Hematocrit	Ketones
Chloride	Hemoglobin	Leukocyte Esterase
Creatinine	Leukocytes	Nitrite
Gamma-glutamyl Transferase (GGT)	Mean Corpuscular Hemoglobin (MCH)	рН
Lactate Dehydrogenase (LDH)	Mean Corpuscular Hemoglobin Concentration (MCHC)	Protein
Phosphate	Mean Corpuscular Volume (MCV)	Specific Gravity
Potassium	Platelet Count	Urinalysis Blood
Serum Glutamic Oxaloacetic Transaminase (SGOT)		Urobilinogen
Serum Glutamic Pyruvic Transaminase (SGPT)		
Serum Iron and Transferrin		
Sodium		
Total Bilirubin		
Total Proteins		
Urea (blood urea nitrogen)		
Uric Acid		

• Chemistry, Hematology, and Urinalysis:

The increases in alanine aminotransferase (ALT), aspartate aminotransferase (AST), and total bilirubin will be examined for liver function. The count and percentage of the increases will be tabulated for each visit including baseline. The increases of ALT and AST will be examined in three categories, i.e. $>2 \times$ upper limit of normal (ULN), $>3 \times$ ULN, and $>5 \times$ ULN, and that of total bilirubin combined with ALT or AST increases will be examined in 1 category, total bilirubin $>3 \times$ ULN and ALT or AST $>2 \times$ ULN.

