9.11 Fundoscopy

The fundoscopy examination is done at the end of the first year of the OLE period and performed if there is any clinical sign of intracranial hypertension. The number and percentage of patients who have fundoscopy done in each 12 month period, and the number and percentage of patients who have signs of intracranial hypertension in each period will be presented.

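### SAP 9.6 summarises laboratory abnormalities per 12-month period while routine draws per year run 4, 1, 3 and 2, so the percentages are not comparable across the dose switch and the PEN transition

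*SAP*

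**What the plan says.** SAP 9.6 plans three laboratory outputs:

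- descriptive statistics at each visit (Tables 14.5.1.1 to 14.5.6.1);
- abnormal results by year (Tables 14.5.1.2 to 14.5.6.2): "Summary of abnormal results (reported as low, high, clinically significant) will be provided for each 12 month period". Percentages are taken over everyone who started that period, tested or not;
- ALT, AST and bilirubin elevations in multiples of the upper limit of normal, counted at every visit (Table 14.5.7).

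For the second output, 9.6 does not say whether a patient counts once or each abnormal result counts. The once-per-patient, any-result rule is written only for IGF-1 SDS, in SAP 9.4.

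Under SAP 6, "all data from Periods III and IV will be presented in 12 month intervals", starting from the first Period III dose. Period V is reported separately, with the pre-dose PEN V1 data as baseline.

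The testing schedule changes between periods:

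- Period III (Protocol 5.2, Appendix 2): "For these patients, study visits will take place every 3 months, starting at visit 3 OLE". Glucose metabolism, thyroid and cortisol, lipids and routine safety tests are done at each visit.
- Period IV (Protocol 5.3, Appendix 3): "Once a year, patients will be required to attend another visit", held on the dosing day, and these panels are drawn there.
- PEN year 1 (SAP 4.3 footnote to these panels): "Data collected every 3 months with the exception of month 9".
- Later PEN years (Protocol 5.4.2): "In addition, the following will be conducted every 6 months, on month 6 and month 12 visits".

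**The concern.** The chance that a child shows at least one out-of-range value in a year grows with the number of samples taken. A percentage per 12-month period over all patients who started it therefore mixes the abnormality rate with the intensity of testing.

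The change in intensity falls at awkward points. Testing is sparsest in Period IV, when the two lower-dose cohorts move to 0.66 mg/kg/week. It becomes denser again when the PEN starts. Safety is the primary objective of the extension analysis (SAP 3.1.1), laboratory parameters are listed endpoints (SAP 3.2.1), and these are the two transitions a reader will want to examine. Compared year by year, the percentages would fall and then rise even if nothing had changed in the children.

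**Working it through.** **Step 1: count the scheduled draws, k.** Protocol and SAP flow charts agree on the routine counts.

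| Reporting year | Scheduled months | k |
|---|---|---|
| Period III | 3, 6, 9, 12 | 4 |
| Period IV year | annual dosing-day visit | 1 |
| PEN year 1, after PEN V1 | 3, 6, 12 | 3 |
| Later PEN year | 6, 12 | 2 |

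Exceptions:

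- Children who had Genotropin in the main study also attend Day 1 and Month 1 in OLE year 1 (Appendix 2), so k is up to 6, or 5 if Day 1 is treated as the period's baseline.
- Children switching to 0.66 mg/kg/week have one more glucose and routine-safety draw at 3 months (Protocol 5.3), so k = 2 for those panels in the switch year. Thyroid, cortisol and lipids stay at 1. If the switch is made at a month 9 visit, the follow-up is held on a dosing day and appears to coincide with the annual draw.
- Lp(a), gonadal hormones and free T3 follow other schedules.

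**Step 2: assumptions.** The documents give no abnormality rate, no correlation and no expected percentage, so there is no figure of the plan's own to reproduce. I assume a constant probability p that one analyte is out of range at a test, and that a child counts once for any abnormal result in the year.

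**Step 3: independent tests.** P(any abnormal) = 1 − (1 − p)^k. At p = 5%:

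- k = 4: 1 − 0.95⁴ = 18.5%
- k = 1: 5.0%
- k = 3: 1 − 0.95³ = 14.3%
- k = 2: 1 − 0.95² = 9.8%

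**Step 4: correlated tests.** Take a beta-binomial with result-level correlation ρ, a = p(1 − ρ)/ρ and b = (1 − p)(1 − ρ)/ρ. Then P(any abnormal) = 1 − ∏(b + i)/(a + b + i), for i = 0 to k − 1. At p = 5% and ρ = 0.5, a = 0.05 and b = 0.95:

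- k = 2: 1 − 0.95 × 1.95/2 = 7.4%
- k = 3: 1 − 0.95 × (1.95/2) × (2.95/3) = 8.9%
- k = 4: 1 − 0.95 × (1.95/2) × (2.95/3) × (3.95/4) = 10.1%

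**Results, % of children with any abnormal result:**

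| p, ρ | Period III | Period IV | PEN year 1 | Later PEN |
|---|---|---|---|---|
| 2%, 0 | 7.8 | 2.0 | 5.9 | 4.0 |
| 5%, 0 | 18.5 | 5.0 | 14.3 | 9.8 |
| 10%, 0 | 34.4 | 10.0 | 27.1 | 19.0 |
| 5%, 0.5 | 10.1 | 5.0 | 8.9 | 7.4 |
| 5%, 0.8 | 6.8 | 5.0 | 6.5 | 6.0 |

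For switchers' glucose and routine-safety panels, the Period IV entry at p = 5% is 9.8% (ρ = 0) or 7.4% (ρ = 0.5), not 5.0%. The pattern disappears only if abnormalities are fully persistent (ρ = 1).

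**Step 5: how large a real change could be offset.** With independent tests, a one-draw Period IV year matches Period III's 18.5% only if the per-test rate rises from 5% to 18.5%, which is 18.5/5.0 = 3.7-fold. With two draws, (1 − p′)² = 0.95⁴ gives p′ = 1 − 0.95² = 9.75%, a near doubling.

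**Step 6: the other counting rule.** If every abnormal result counts, the expected number per 100 children is 100kp: 20, 5, 15 and 10 at p = 5%. The Period III to Period IV ratio is then 4.0 instead of 3.7, so the effect is larger.

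**The case against.** The best defence is that SAP 9.6 already gives by-visit descriptive statistics for every panel and by-visit counts of ALT, AST and bilirubin elevations, supported by figures and listings. These do not depend on the number of draws in a year. That stands, and it narrows the point. A reader might infer that a real rise at the dose switch would go unseen, or that a PEN signal would be manufactured. The documents do not support so strong a claim, because a shift could still appear in the by-visit means and listings. What remains exposed is the low, high and clinically significant percentages, which for other analytes are promised only per period.

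Other tempting readings also go too far:

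- *That the SAP counts any abnormal result once per child, or sets the periods side by side in one table.* Section 9.6 has no counting rule, and SAP 11.1 lists table titles without layouts.
- *That every child has one draw in Period IV.* Those whose dose rises generally have two glucose and routine-safety draws in the switch year, and Cohort 3 has no dose rise. Transition dates also varied (SAP 4 and 6), so a reporting year need not coincide with Period IV.
- *That fundoscopy has the same defect.* SAP 9.11 does describe a changing schedule: "The fundoscopy examination is done at the end of the first year of the OLE period and performed if there is any clinical sign". But it also reports the number examined in each period and promises no trend.

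It is also fair to say that the size rests on assumed values. At high correlation the spread is modest: 6.8, 5.0, 6.5 and 6.0% at ρ = 0.8. The direction does not depend on those values for any correlation below 1.

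**Conclusion.** The point holds for the per-period abnormality summaries in SAP 9.6, apart from the by-visit liver counts. With draws at 4, 1, 3 and 2 per year and no standardisation for testing, those percentages are not comparable across the move to 0.66 mg/kg/week or the change to the PEN.

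At an assumed constant 5% per test, with each child counted once, the schedule alone makes the Period III figure about 3.7 times that of a one-draw Period IV year under independence, and about twice it (10.1/5.0) at correlation 0.5. For switchers' glucose and routine-safety panels the independent-test ratio is about 1.9 (18.5/9.8). The analysis is descriptive, so no test or error rate is affected. What is at risk is the reading of a safety table on the extension's primary objective.

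**What to change.** In SAP 9.6, tabulate low, high and clinically significant results at each scheduled visit over patients with a result at that visit, as is already planned by visit for ALT, AST and bilirubin. Use this table for any comparison across years.

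Label each visit with its post-dose day. The month-12 sample alone would not be a like-for-like comparator: it is taken about day 4 in Period III (Protocol 5.2), on the dosing day in Period IV (5.3), pre-dose on the dosing day in PEN year 1 (5.4.1.5), and on day 4 (−1) from PEN year 2 (5.4.2).

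Keep the per-period summary as supplementary, with its counting rule stated and the number of tests per child printed beside each percentage. SAP 9.11 needs no change.

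The cost is SAP wording and table shells, with no new data. The tables become slightly longer. Because SAP 7.4 keeps unscheduled assessments out of visit summaries, unscheduled abnormal results would appear only in the supplementary summary and the listings.

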5.7.1.3 Indicators of lipid metabolism

In GHD patients, administration of GH has resulted in lipid mobilization, reduction in body fat stores, and increase in plasma fatty acids. However there still exists a slight controversy about potential atherogenic effects of chronic GH replacement therapy. Parameters that will be assessed in this protocol are: total cholesterol, HDL-cholesterol, LDL-cholesterol triglycerides and Lp(a) lipoprotein (Lp(a) lipoprotein will not be measured in the LT-OLE-PEN period). Monitoring of changes in lipid metabolism may be meaningful from two aspects, as an indicator of atherogenesis and as an indicator of insulin resistance. Lp(a) lipoprotein has been selected as a potentially challenging parameter. Previously there were reports indicating that Lp(a) lipoprotein, as well as the risk of atherogenesis increase under the treatment of r-hGH (Mooser V, 1997) (Olivcrona H, 1993), however there were several publications confirming that Lp(a) doesn't change during the GH treatment (Hassan HMS, 1995) (Hassan HMS, 1996).

OPKO Biologics	Protocol for Clinical Study CP-4-004	Page 69 of 133
Effective Date: Date of final electronic approval		

One explanation for these contradictory findings could be the high variability of the assays used (Wieringa G, 2000), however the effects of sustained release and long-acting growth hormones have not been sufficiently investigated.

Indicators of lipid metabolism will be assessed according to the schedule in [Appendix 1: Schedule of Assessments – Main Study](#) to [Appendix 5](#).

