9.4 IGF-1 and IGF-1 SDS

IGF-1 will be listed for each patient, but not summarized. IGF-1 SDS will be listed, and summarized at each visit. In addition, the number and proportion of patients with IGF-1 SDS > 2 will be summarized. The denominator will be the number of patients with results at each visit. For the summaries of each 12 month period with multiple visits, each patient will be counted once, and will be counted as having IGF-1 SDS >2 if any results within that summarized interval is >2. IGF-1 SDS will also be summarized by ADA status.

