9.9 ECG

The ECG parameters (heart rate, PR interval, QRS interval, QT interval, RR intervals, QTc-_{Bazett} interval) will be listed. The clinical assessments: Normal / Abnormal – same as screening / Abnormal – new, clinically not significant / Abnormal – new, clinically significant or aggravated, collected at the end of each OLE and PEN year will be summarized as proportion of patients with each assessment, with the number of patients at the beginning of the period as the denominator.

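### Period-level laboratory and ECG percentages are divided by every child who entered the period, tested or not, so they run low wherever some have no result

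*SAP*

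**What the plan says.** - **Laboratory tests (SAP 9.6).** A summary of abnormal results "will be provided for each 12 month period, with the number of patients at the beginning of each period for the denominator".
- **ECG (SAP 9.9).** The clinical assessment, made once at the end of each OLE or PEN year, is "summarized as proportion of patients with each assessment, with the number of patients at the beginning of the period as the denominator".
- **Missing data (SAP 7.4).** In general nothing is imputed. The listed exceptions are adverse-event attributes and partial dates, not laboratory or ECG results.
- **A different rule elsewhere (SAP 9.4).** For IGF-1 SDS above 2: "The denominator will be the number of patients with results at each visit".
- **Tests to be reported (SAP 9.6).** The list has no limit by period. It includes T3, Lipoprotein-A and rows labelled by age and sex, such as "Females >=12 y.o.: FSH, LH and estradiol".
- **What is actually measured.** Protocol 5.7.1.3 states that "Lp(a) lipoprotein will not be measured in the LT-OLE-PEN period". Protocol 5.7.1.4 confines the gonadotrophic hormones to the LT-OLE and LT-OLE-PEN periods, in girls from 12 and boys from 13. For later PEN years Protocol 5.4.2 lists "other hormonal levels (TSH, free T4, cortisol", without T3. The SAP 4.3 chart for the first PEN year shows "Other hormonal levels (TSH, FT4, T3, cortisol".

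**The concern.** A child without a result can never enter the numerator but always sits in the denominator. The error therefore has one direction: towards fewer abnormalities. Safety in extended treatment is the primary objective of this SAP (3.1.1), and the affected tables (14.5.1.2 to 14.5.6.2 and 14.6.3.2) are part of the core safety output. A laboratory table that shows only abnormal results gives the reader no sign of how many children were tested. If a test is not scheduled at all in a period, the rule yields zero over the number who entered, which reads as reassurance rather than as absence of data.

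**Working it through.** The plan states no abnormality rate for these tables, so there is no figure to reproduce.

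**Inputs.** Children starting the OLE: 53 (SAP 4.1), the largest possible number entering any year. Numbers tested and true abnormality rates are not given. The values below are assumptions: 0 to 53 tested, with 5% to 20% abnormal among those tested.

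**Formula.** With x abnormal, n tested and N entered:

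printed rate = x/N = (x/n) × (n/N)

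The SAP rule thus multiplies the rate among tested children by the share tested. The two agree only when n = N.

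**Sensitivity to the number tested**, with N = 53 and a true rate of 10%:

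| Tested | 53 | 50 | 45 | 40 | 30 | 20 | 10 | 0 |
|---|---|---|---|---|---|---|---|---|
| Printed | 10.0% | 9.4% | 8.5% | 7.5% | 5.7% | 3.8% | 1.9% | 0.0% |

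With 40 tested, true rates of 5% and 20% would print as 3.8% and 15.1%.

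**Whole-number examples**, N = 53:

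| Abnormal / tested | SAP rule | Tested denominator |
|---|---|---|
| 4 / 45 | 4/53 = 7.5% | 8.9% |
| 4 / 40 | 4/53 = 7.5% | 10.0% |
| 3 / 15 | 3/53 = 5.7% | 20.0% |
| 2 / 10 | 2/53 = 3.8% | 20.0% |
| 0 / 0 | 0/53 = 0.0% | not evaluable |

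**Where the schedule itself leaves children untested.**

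1. *Routine laboratory tests, Period III and PEN.* These are done at months 3, 6, 9 and 12 in Period III (Protocol Appendix 2). In the first PEN year they are done at PEN V1 and months 3, 6 and 12 (Appendix 4), and at months 6 and 12 after that (Appendix 5). Few children should have no result all year.
2. *Period IV laboratory tests.* Most panels are done only at month 12, apart from the visit after a dose switch, the visit after a treatment gap and early termination (Appendix 3).
3. *ECG.* It is done only at month 12 of each year. PEN V1 includes no ECG (Appendix 4), and SAP 4 says that the month of transition to PEN varies. A child who moves to PEN before month 12 of an OLE year is counted as entering that year but has no ECG scheduled in it. No early-termination visit fills the gap, because the child has not left the study.
4. *Gonadal hormones.* Entry age was at most 10 for girls and 11 for boys (Protocol 4.1). Month 12 of OLE year 2 is about 3 years after entry, ignoring treatment gaps. Only girls who entered at about 12 − 3 = 9 or older, and boys at about 13 − 3 = 10 or older, would then be tested. Testosterone and estradiol are each measured in one sex only.
5. *Nobody scheduled.* Lp(a) in PEN, and gonadal hormones in OLE year 1, compute to 0/N. For T3 in PEN the result depends on which schedule applies. The Protocol omits T3, the SAP's first-year PEN chart includes it, and the SAP's chart from the second PEN year omits it.

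**The case against.** A reader might infer several stronger claims that the documents do not support.

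- *That laboratory rates are seriously understated throughout.* Routine testing in Period III and PEN is frequent. Early-termination visits follow the month 12 assessments (Protocol 5.5.2), and SAP 7.4 keeps their results in the annual interval. Leavers are therefore scheduled for the tests they would otherwise miss.
- *That the bias builds up as children leave over the years.* The denominator is reset at each period, so only children untested within that same period matter.
- *That an untested child is counted as having a normal ECG.* Normal is its own category in SAP 9.9. An untested child falls in none, and the shortfall from 100% partly reveals the gap.
- *That the tables will print 0% for tests not done.* The SAP does not say that such a row appears, and a programmer might suppress it. Zero is simply what the stated rule computes.
- *That SAP 9.4 sets a precedent for period-level tables.* Its stated denominator is per visit. For the 12-month summary it counts each child once and does not restate the denominator.

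Two further points have weight. Using the children who entered is this plan's usual period-level convention (adverse events in 9.1, injection-site scores in 9.3, dose adjustments in 9.13). The gonadal rows carry an age and sex label, so someone could apply the denominator within that group. But adverse events are collected on everyone, which is not so for an annual ECG or an age-restricted hormone. For injection-site scores, 9.3 sets missing values to the worst grade, whereas 9.6 and 9.9 have no such rule. And 9.6 makes no exception for the labelled rows.

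**Conclusion.** The point holds in a limited form. SAP 9.6 and 9.9 state a denominator that makes each percentage the rate among tested children times the share tested. It is understated wherever some who entered have no result. The effect is probably small for routine laboratory tests in Period III and PEN. It is material for annual Period IV laboratory tests and ECG, and largest for gonadal hormones. For Lp(a) in PEN and gonadal hormones in OLE year 1 the rule gives 0/N with no one scheduled for testing.

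The actual size cannot be calculated, because numbers tested are not given; the illustrations rest on assumed counts. This should be fixed but is not critical. The analysis is descriptive with no hypothesis test, by-visit laboratory summaries are planned, and individual results are listed (Listings 16.2.8.4 to 16.2.8.11 and 16.2.9.3).

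**What to change.** In SAP 9.6 and 9.9:

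1. Use as denominator the children with at least one post-baseline result for that analyte, or with an ECG, in the period. Post-baseline is needed because 9.6 takes the first visit of each period as baseline. A child with only that sample has not been followed for a new abnormality.
2. For gonadal hormones, restrict the denominator further to the eligible age and sex.
3. Show the number tested beside the number who entered in every row.
4. Print *not assessed* where no test was scheduled, such as Lp(a) in PEN and gonadal hormones in OLE year 1.
5. Reconcile T3 in the SAP's first-year PEN flow chart with the Protocol's PEN schedule (5.4.1 and Appendix 4) and with the SAP's own chart for later PEN years.

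The cost is SAP wording and a denominator change in the table programs. No new data are needed and conduct does not change. The downside is that some percentages become less favourable and the denominator varies by analyte.
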